The primary aim is: To evaluate the safety and tolerability of fecal transplant through rectal and oral capsular routes in cirrhosis and HE from a liver disease and symptom standpoint using analysis of serious adverse events, especially HE recurrence, in a placebo-controlled trial.

Secondary aims are between the groups:

- 1. Safety and tolerability of FMT compared to placebo
 - a. Frequency, severity and relatedness of solicited and unsolicited AEs through day 30
 - b. Occurrence of new potentially transmitted infections through six-months post FMT
 - c. Occurrence of new onset or significant worsening of chronic medical conditions post-FMT
- 2. To define the changes in microbiota composition and function of the stool microbiota after FMT compared to pre-FMT baseline and donor compared to placebo

- 3. To evaluate changes in systemic inflammatory cytokines and endotoxin, quality of life and cognitive function compared to pre-FMT baseline and compared to placebo
- 4. To determine occurrence of new onset or significant worsening of chronic medical conditions through six months post-FMT and compared to placebo
- 5. To evaluate the changes in the microbiota after the second oral FMT vs. placebo compared to baseline values

Inclusion/Exclusion Criteria:

Inclusion criteria:

- A. Cirrhosis diagnosed by either of the following in a patient with chronic liver disease
 - a. Liver Biopsy
 - b. Radiologic evidence of varices, cirrhosis or portal hypertension
 - c. Laboratory evidence of platelet count <100,000 or AST/ALT ratio>1
 - d. Endoscopic evidence of varices or portal gastropathy
 - e. Fibroscan values suggestive of cirrhosis
- B. On treatment for hepatic encephalopathy (patient can be on lactulose and rifaximin)
- C. Age: at least 21 years of age
- D. Able to give written, informed consent (demonstrated by mini-mental status exam>25 at the time of consenting)
- E. Women of child bearing potential must agree to use effective contraception for the duration of the study and for 10 days prior and 30 days after the study
- F. Negative pregnancy test in women of childbearing age

Exclusion criteria:

- A. MELD score >22
- B. WBC count <1000 cells/mm3
- C. Platelet count < 25,000/mm3
- D. TIPS in place for less than a month
- E. Currently on antibiotics apart from rifaximin
- F. Infection at the time of the FMT (diagnosed by blood culture positivity, urinalysis, paracentesis as needed)

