Specific safety findings will result in temporarily suspending enrollment until a safety review is convened, the objective of which is to determine whether the study should continue per protocol, proceed with caution, be further investigated, be discontinued, or be modified and then proceed. Suspension of enrollment is another potential outcome of a safety review. This will be done if the assigned infection is in the FMT group since this patient population is prone to infections.

Subsequent review of serious, unexpected, and related AEs by the Data and Safety Monitoring Board, IRB, the PI, or the FDA or relevant local regulatory authorities may also result in suspension of further trial interventions/administration of FMT at a site. The FDA and PI retain the authority to suspend additional enrollment and study interventions/administration of FMT for the entire study, as applicable. The PI and the adjudication panel will make the initial decision. The subsequent safety review by the IRB and FDA will then decide if the study can resume.

Findings that will trigger a safety review are

Findings that will trigger a safety review are

- o Death related to FMT material or study procedures in any subject;
- New potentially transmitted infection in five or more subjects assigned to FMT - i.e., cannot exdude transmission and/or attribution is

pending investigation/Data Monitoring Committee (DMC) adjudication;

- Any single potential transmitted infection assessed as possibly, probably, or definitely related to FMT by the investigator and DMC.
- One or more subjects assigned to FMT has a serious, unexpected AE assessed as possibly, probably, or definitely related to FMT by the investigator and DMC; Five or more subjects (per assigned group) develop a new diagnosis of a medical condition or immune-mediated disease considered probably, or definitely related to FMT.
- Five or more severe AEs of a similar nature occurring in different subjects and assessed as definite, possible or probable relatedness to study product in groups assigned to FMT (per assigned group)

FDA/CBER will be notified by phone or fax within 72 hours if the study is halted for review.

Individual study halting rules

- (1) patient's choice
- (2) change in GI adverse events with a magnitude of 3 increase over baseline
- (3) fever and signs of infection (including WBC count >12,000/ml)
- (4) SAE development including cirrhosis complications (OHE) and hospitalizations for

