- any cause including bleeding, nausea, vomiting, or other GI conditions
- (5) increase in MELD score by 8 or more
- (6) Increase in AST, ALT or Alkaline phosphatase to 10X ULN
- (7) Non-elective Hospitalization

Even if the subject is withdrawn before 30 days, they will still be followed till 6 months for safety.

Health risks (please see adverse events table attached):

Adverse events will be both for the FMT material, placebo as well as for the procedures. These risks are listed in the Risk Section of the informed consent.

These possible adverse events will be:

- (a) Fever: yes or no answer with grading based on actual temperature on examination
- (b) diarrhea (will be asked to grade them from 0-4 compared to baseline)
- (c) abdominal cramping and pain (will be asked to grade them from 0-4 compared to baseline)
- (d) vomiting (will be asked to grade them from 0-4 compared to baseline)
- (e) Development of HE (Altered mental status) in every group: will be monitored by clinical examination through the West-Haven Criteria²⁵. We will be closely monitoring all subjects for this development, including a clinical examination by a gastroenterologist at every visit.

(f) Development of infections specifically spontaneous bacterial peritonitis -Fever will be reconfirmed by measuring by the study nurse and if it is confirmed, a detailed investigation into the cause of the fever will be performed as part of standard clinical care and the patient will be withdrawn from the study.

-Vomiting, constipation, GI bleeding, abdominal cramps and diarrhea: If the patient's diarrhea and abdominal cramps change in a magnitude of 3 over their baseline values per the AE chart (patients with cirrhosis often have these symptoms at baseline), they will be withdrawn from the study.

-Infections that occur in the FMT group will be thoroughly investigated according to standard clinical care to prove whether they were associated with the FMT.

Adverse Event Grading Chart

 Volunteer Study ID:
 Date:
 Time:

 Study Start Date:
 Current Visit number:

*Volunteer's responses will be marked on grading sheet by circling the appropriate grade or indicating no symptoms.

PARAMETER COMPARED TO BASELINE	GRADE 1 MILD	GRADE 2 MODERATE	GRADE 3 SEVERE	GRADE 4 POTENTIALLY LIFE-THREATENING
ESTIMATING SEVERITY	(GRADE		•	•

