Dehydration	Increased oral fluids indicated; dry mucous membranes; diminished skin turgor	IV fluids indicated <24 hours	IV fluids indicated >24 hours	Life-threatening consequences (e.g. hemodynamic collapse)
Constipation	NA	Persistent constipation requiring regular use of dietary modifications, laxatives, or enemas	Obstipation with manual evacuation indicated	Life-threatening consequences (e.g., obstruction)
Procedural Enema	Rectal discomfort; minor bleeding <24 hours on toilet paper	Rectal discomfort; minor bleeding >24 hours on toilet paper	Gross hematochezia	Bowel perforation
Change in mental status (West-Haven Criteria)	No change in orientation and no asterixis	Disorientation to time, asterixis	Disorientation to place or person, asterixis, lethargy and stupor	Coma
MELD score increase (includes INR, bilirubin and creatinine)	<3	3-7	>8	NA
Serum WBC	NA	NA	>12,000/ml or <1000/ml	NA
AST	NA	≥ 5.0 to < 10.0 x ULN	≥ 10.0 x ULN	NA
ALT	NA	≥ 5.0 to < 10.0 x ULN	≥ 10.0 x ULN	NA
Alkaline phosphatase	NA	≥ 5.0 to < 10.0 x ULN	≥ 10.0 x ULN	NA

Specific investigation of the infection related to the FMT in those assigned to the FMT group:

- 1. Regular clinical care of the subject according to the infection developed will include the appropriate cultures and relevant antibiotics will be started
- 2. Stool tests from the patient will be compared to the donor safety sample when a CLIA-

certified assay is available

3. Contact will be made with the FMT suppliers to evaluate this batch of the donor. Specifically, the cross-referenced drug master file has the means to track down the lots and batches of the donors. In the event of a suspected adverse event related to the potential transmission of an infection, an immediate initial consultation will be held between the researchers and the Chief Medical Officer of Molecular and Cellular Therapeutics (GMP) facility at the University of Minnesota ([name]) to gather further information. This will be followed by a detailed collaborative investigation as follows:

The investigation will entail:

a. Strict donor material quarantining during the investigation

b. Rescreening of the donor safety aliquot and the donor for infectious diseases as well as risk factors for the suspected infectious disease

c. Consultation with external experts in infectious diseases and gastroenterology with extensive experience in FMT.

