d. Full Advisory board review at Molecular and Cellular Therapeutics (GMP) facility at the University of Minnesota to track the donors

Laboratory:

Lab values for WBC counts, serum AST, ALT, Alkaline phosphatase, serum bilirubin, INR and serum creatinine (all three are in MELD score) will be followed.

These criteria will be graded per the chart as well.

The lab values that will be followed from an adverse event perspective will be:

- WBC count: a new >12,000/ml or <1000/ml in the presence of fever will necessitate investigation of an infectious source
- Worsening of the MELD score by 8 or higher will be considered significant
- Increase in AST, ALT and alkaline phosphatase >10 ULN will be considered significant although this change is not expected in cirrhotic subjects

[name] asks subjects to allow him to keep a portion of their blood, urine and stool specimens collected during the study to be used for future testing. Subjects agreeing to this will have a portion of their blood, urine and stool specimens stored in a research laboratory at the McGuire DVAMC. The samples will be de-identified. This means that no information that can identify a subject will appear on the samples. Subjects do not have to agree to this in order to participate in the study. If at any time during or after the study, a subject decides they want their samples destroyed, the subject can contact [name] at [contact] and request that their samples be destroyed.

Adverse Events Reporting

[name] will function as both the Investigator and the Sponsor during the conduct of this study. [name] will be responsible for reporting all safety observations (adverse events and serious adverse events) to the FDA

A. Definitions

1. Adverse Event (AE)

An AE is any untoward medical occurrence in a patient or study subject administered FMT due to the material or procedure that does not necessarily have a causal relationship with this treatment. An AE can therefore be any unfavorable and unintended sign (including an abnormal laboratory finding), symptom, or disease temporally associated with the use of a FMT, whether or not related to the FMT.

• AEs may be new events or may be pre-existing conditions that have become aggravated or have worsened in severity or frequency.

• AEs may be clinically significant changes from baseline in physical examination, laboratory tests, or other diagnostic investigation (e.g. laboratory results, radiographic findings).

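### As the text reads, the WBC limits in the AE chart, individual halting rule 3 and the laboratory rule are per ml, 1000-fold below the evident per-mm3 intent (minor; check the source page first)

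*Combined protocol and SAP*

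**What the plan says.** Three operative places in the combined protocol and SAP give WBC limits per ml:

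- **Adverse Event Grading Chart, Serum WBC row.** Grade 3 is ">12,000/ml or <1000/ml". No other grade is defined, and the row carries no fever condition.
- **Individual study halting rules, item 3.** The ground is "fever and signs of infection (including WBC count >12,000/ml". Only the upper limit appears here.
- **Laboratory.** The rule reads "WBC count: a new >12,000/ml or <1000/ml in the presence of fever will necessitate investigation of an infectious source". The same section ties laboratory values to the chart: "These criteria will be graded per the chart as well".

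The exclusion criteria state blood counts on a different scale. Criterion B is "WBC count <1000 cells/mm3" and criterion C is "Platelet count < 25,000/mm3".

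The background account of the earlier enema trial also gives its WBC limits per ml, but that sentence reports past results and sets no rule. Nothing in the document explains a per-ml scale for WBC or restates the unit.

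**The concern.** The figure 1000 appears for the same analyte with two units that differ by a factor of 1000. Both cannot be meant. The eligibility criterion gives a workable limit. The per-ml version gives limits that no eligible patient could fall between.

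These are working safety limits that decide a severity grade, contribute to a ground for stopping a subject, and call for an infection work-up. If the unit is wrong on the page, the WBC part of each rule carries no information when applied as written, and the rule works only if the reader silently corrects it.

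**Working it through.** **Inputs.** Upper limit 12,000/ml (chart, halting rule 3, Laboratory). Lower limit 1000/ml (chart, Laboratory). Eligibility floor 1000 cells/mm3 (exclusion B). Conversion: 1 ml = 1000 mm3, so count per mm3 = count per ml ÷ 1000.

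**Step 1. Written limits on the eligibility scale.**
- Upper: 12,000 ÷ 1000 = 12 cells/mm3.
- Lower: 1000 ÷ 1000 = 1 cell/mm3.

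**Step 2. Eligibility floor on the written scale.**
- 1000 × 1000 = 1,000,000/ml.
- Against the upper limit: 1,000,000 ÷ 12,000 = 83.3.
- Against the lower limit: 1,000,000 ÷ 1000 = 1000.

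Every eligible count therefore starts at least 83 times above the written upper limit. Even from the floor, a count would have to fall by more than 1 − 1/1000 = 99.9% to go below the written lower limit.

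**Step 3. What each rule does if read literally.**
- *Halting rule 3.* The WBC sign is always present, so it adds nothing to fever.
- *Laboratory rule.* It asks for a new value. A count that was above the limit at entry is not newly above it, so the upper limit does not fire, and the lower limit is out of reach.
- *Chart.* Every count is Grade 3 if the row is taken alone. None is, in practice, if the row is read as a change from baseline. Neither reading discriminates.

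**Step 4. The same figures per mm3.** The upper limit becomes 12,000/mm3 (12,000,000/ml). The lower becomes 1000/mm3 (1,000,000/ml), which is exactly the figure in exclusion B. The document is then consistent on this analyte.

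**The case against.** The strongest objection is that the unit may not be the author's. A micro sign read as the letter m would turn a per-microlitre unit into /ml. A microlitre is a cubic millimetre, so the limits would then be correct. Repetition of /ml across sections does not settle this, since a systematic misreading and a repeated typing habit look the same. A reader might infer from the Greek letters that did come through elsewhere that no such loss occurred. The document does not support that inference: interleukin-1 beta is printed with a plain b in the same parts of the text, and other words and figures near the disputed rules are visibly garbled. This objection stands as a reason to look at the source page first.

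The second objection is that little follows in practice, and this largely stands. The background account reports no significant laboratory changes by limits in the same wording, which fits a team that reads them per mm3. Halting rule 3 and the Laboratory rule both involve fever, and the Health risks section already provides that for confirmed fever "a detailed investigation into the cause of the fever will be performed as part of standard clinical care and the patient will be withdrawn". The chart row has no such backstop, but its severity grades are headed as comparisons with baseline.

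Two stronger readings are tempting:

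- A reader might infer that every subject would be recorded with a severe AE from baseline, or that the rule on five similar severe AEs would force a safety review. The document does not support this. In the AE definitions, "AEs may be clinically significant changes from baseline in physical examination, laboratory tests, or other diagnostic investigation", so an unchanged normal count is not an event. The review trigger also needs an assessment of relatedness to study product.
- A reader might infer that the different WBC figures at Visit 3 are part of the same error. They carry no unit, and they prompt attention rather than assign a grade. Any conflict would rest on an assumed unit, and it is a separate matter.

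**Conclusion.** The point holds as a minor error in the text as it reads: WBC limits in three operative places are per ml, 1000-fold below the evident intent. The intended unit is inferred from exclusion B, which uses the same figure for the same analyte, and from the platelet limit beside it; no outside source is needed. The literal limits of 12 and 1 cells/mm3 cannot separate patients.

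The conclusion assumes that the source page really shows /ml, which could not be confirmed here. If it shows a per-microlitre unit, there is no error in the plan. It also assumes, on the size of the effect, that staff read the limits per mm3, which is probable but not stated. The document does not support any claim of patient harm or false halting, or any effect on eligibility, sample size, power or the primary endpoint.

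**What to change.** Check the source page for a micro sign at the three places. Unless it is there, replace /ml with /mm3 in the Serum WBC row of the Adverse Event Grading Chart, in individual halting rule 3, and in the WBC item of the Laboratory section. The numbers themselves stay as they are. The cost is a short look at the original and an editorial correction in three places, with no change to procedures, data collection or analysis.

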None of the Veterans included in this study will have any visits at VCU. Non-Veterans will be recruited according the approved VCU protocol and will sign the VCU consent. These potential participants will also be shown the approved VA Consent form in order to provide them the full scope of the study. These non-Veterans will have a choice to perform all subsequent studies at VAMC or only the 2 treatment visits, which are visits 2 and 4. When they first arrive at the VAMC for their in-person visits, they will be asked to sign the VA IRB approved consent form before proceeding. Neither of the treatment visits will be performed at VCU even if the enrollee is a non-Veteran.

[name], who is the PI at both sites, will ensure that subjects meet criteria for enrollment and reporting to both IRBs as necessary. An MOU will be signed.

Safety and hospitalization analysis:

Using detailed FDA-approved protocols, patients will be adjudged based on adverse events and serious adverse events at every visit and during the 6-month follow-up. Any SAEs or deaths in an FMT-randomized group will require the DMC to define the "relatedness" of the event to the FMT. If the DMC votes that this is related to the FMT, then this will be sent to the FDA, and Molecular and Cellular Therapeutics (GMP) facility at the University of Minnesota to invoke stopping rules as detailed below. The safety endpoints will be all-cause hospitalizations, defined as unplanned, non-elective hospitalizations within the 6-month period. The reason for the hospitalization will be analyzed by the investigating team and divided into liver-related, liver-unrelated, planned or elective. The latter two categories will not count towards the study but the first two will be analyzed by the team and submitted to the DMC. Other SAEs will be analyzed per FDA definitions. AEs that do not meet the standards of SAE will be evaluated at each visit and be compiled to define trends in one group compared to the other.

Reasonably foreseeable significant risks:

Physical risks:

- 1. Infection or bruising during blood draw
- 2. Procedure-related adverse events from enema (e.g. perforation, bleeding etc)
- 3. Pill-associated dysphagia
- 4. FMT material-related adverse events (e.g. transmissible infection, allergic reaction)

Psychological/Social risks:

(b) Very small risk of loss of confidentiality and privacy

Specific issues to be captured will be

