1. Assessment of Severity will be performed compared to baseline symptoms that the patient has at enrollment and according to the adverse event table The severity of AEs will be assessed according to the following definitions:

•Mild (1 change): the AE is noticeable to the patient and/or the Investigator, but does not interfere with routine activity

•Moderate (2 change): the AE interferes with routine activity, but responds to symptomatic therapy or rest

•Severe (3 change): the AE significantly limits the patient's ability to perform routine activities despite symptomatic therapy

• Life threatening (4 change): Potentially life-threatening

2. Assessment of Causality

The Investigator must assess the relationship of any AE (including SAEs) to FMT, as *related* or *not related*, based on clinical judgment and using all available information, and may include consideration of the following factors:
Possible alternative causes of the AE, including the disease under treatment, pre-existing conditions, concomitant use of other drugs, and presence of

environmental or genetic factors

• The temporal association between FMT exposure and onset of the AE

• Whether the manifestations of the AE are consistent with known actions or theoretical toxicity of FMT

The causal relationship between FMT and the AE will be assessed using one of the following categories:

Not Related: An AE is not associated with FMT if:

• Temporal relationship is lacking (e.g., the event did not occur within a reasonable time frame following administration of FMT); or

• Other causative factors more likely explain the event (e.g. pre-existing condition, other concomitant treatments);

Related: An AE is attributed to FMT if:

- There is a positive temporal relationship (e.g. the event occurred within a reasonable time frame following FMT); and
- The AE is more likely explained by FMT than by another cause

To aid this assessment, the Investigator/Sponsor will be helped by the VA Central DMC as mentioned above.

All SAEs, possible transmission of infections, and new or worsening medical conditions possibly related to FMT will be referred to this panel, including ones elicited at the monthly visits. This panel will vote based on their analysis of the data regarding the "relatedness" of the AE.

Reporting Safety Observations by the Investigator /Sponsor

1. Reporting of Non-serious AEs

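### The causality code has two categories, but four of the six safety-review triggers read graded terms that the plan neither defines nor maps to that code

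*Combined protocol and SAP*

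**What the plan says.** Three parts of the combined protocol and SAP use a causality judgement to decide what happens next.

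- **Assessment of Adverse Events, 2. Assessment of Causality.** "The Investigator must assess the relationship of any AE (including SAEs) to FMT", as *related* or *not related*. The text continues: "The causal relationship between FMT and the AE will be assessed using one of the following categories". Two categories follow. *Not related* applies if timing does not fit, or if "Other causative factors more likely explain the event". *Related* needs fitting timing and also that "The AE is more likely explained by FMT than by another cause". The same section then says: "All SAEs, possible transmission of infections, and new or worsening medical conditions possibly related to FMT will be referred to this panel", which votes on relatedness.
- **Safety and hospitalization analysis.** "Any SAEs or deaths in an FMT-randomized group will require the DMC to define the" relatedness of the event. "If the DMC votes that this is related to the FMT, then this will be sent to the FDA" and to the manufacturing facility "to invoke stopping rules as detailed below".
- **Overall Study Halting Rules.** Six findings trigger a safety review (printed as five bullets, because two run together). Four are worded in grades of possible, probable and definite.

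The primary endpoint under Endpoints and Plan of Analysis, SAEs related to FMT including HE recurrence within 6 months, rests on the same kind of judgement.

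**The concern.** The only causality scale that the protocol defines has two values and a more-likely-than-not border. The rules that call a safety review are mostly written in a three-grade scale that is not defined. An assessor who follows the causality section exactly does not produce the information that the triggers ask for.

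The cases that fall in the gap are ones the protocol itself expects. It notes that several of the monitored symptoms belong to the course of advanced cirrhosis, and that these patients are susceptible to infection. Events with a competing explanation should therefore not be rare. At stake is which of them formally lead to a review, and which SAEs count as FMT-related in the primary endpoint.

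**Working it through.** No power, alpha or sample-size figure enters this point. The check is a tally of the triggers, followed by a test of whether any reading of the two-way code can operate them.

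**Step 1. The six findings in the Overall Study Halting Rules.**

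| Finding | Causality term | Count needed | Assessor named in the trigger |
|---|---|---|---|
| Death | plain *related* | 1 | none |
| Potentially transmitted infections, transmission not ruled out and/or attribution pending | no grade | 5 subjects | DMC, for pending cases |
| Single potentially transmitted infection | from *possible* | 1 | investigator and DMC |
| Serious unexpected AE | from *possible* | 1 | investigator and DMC |
| New diagnosis | from *probable* | 5 per group | none |
| Similar severe AEs | from *possible* | 5 per group | none |

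Tally: plain *related* 1, no grade 1, from *possible* 3, from *probable* 1; 1 + 1 + 3 + 1 = 6. Graded triggers: 3 + 1 = 4 of 6. Two of the three that start at *possible* need only one case.

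**Step 2. Is there a definition or mapping?** None was found. The adverse event grading chart grades severity, not causality. The causality section uses *possibly related* once, as a condition for referral to the DMC, without defining it. The definition of a suspected adverse reaction uses a reasonable-possibility standard for IND reporting and does not connect it to the grades.

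**Step 3. Can the two-way code run the four graded triggers under some mapping?**

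- Suppose *related* means possible, probable or definite. The three triggers that start at *possible* can then be read from the code. The new-diagnosis trigger cannot, because possible cases would be counted that its wording leaves out. This mapping also contradicts the more-likely test. Triggers operable: 3 of 4.
- Suppose *related* means probable or definite, which is closer to the more-likely test. The new-diagnosis trigger can be read. The other three cannot, because possible cases are hidden among *not related*. Triggers operable: 1 of 4.

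Neither mapping gives 4 of 4. The halting rules treat *possible* and *probable* as different, and one border cannot mark both.

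**Step 4. Two event types.**

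- Timing fits and FMT is plausible, but cirrhosis is the more likely cause. The causality section gives *not related*. In the ordinary sense of possibly, one such potentially transmitted infection, or one such serious unexpected AE, meets the causality wording of a single-case trigger.
- Timing fits, and FMT and another cause are equally likely. *Related* fails because FMT is not the more likely cause. *Not related* fails because the other cause is not more likely either. No category applies.

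**The case against.** The strongest reply is that the halting rules stand on their own. They list findings that suspend enrollment, and two of the graded triggers name the investigator and the DMC, so a separate graded assessment may be intended. The two-way instruction is addressed to the investigator and does not restrict the form of the DMC's vote. That intent is plausible, but the text neither defines such a scale nor tells anyone to record it. The grades might be on the case report forms or in the cross-referenced IND, which are not in the documents.

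Several stronger readings are tempting and are not supported:

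- *A DMC vote of related is the only way into the stopping rules.* The safety and hospitalization section says what follows such a vote. It does not exclude other routes, and the PI and FDA can suspend.
- *Ambiguous events go unseen.* All SAEs, possible transmissions and possibly related conditions go to the DMC. New potentially transmitted infections are reported to the FDA whatever the causality judgement. A suspected transmission brings consultation with the supplier and quarantine of donor material.
- *Two triggers have no assessor.* The causality section makes the investigator the assessor of every AE, and the halting rules give the initial decision to the PI and the adjudication panel. What is missing is the scale.
- *The infection thresholds of five and one contradict each other.* They read naturally as before and after adjudication.
- *The reasonable-possibility standard is an error.* It is a deliberately lower standard for IND reporting.

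What stands is the mismatch of scales, which none of these answers removes.

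**Conclusion.** The point holds in limited form. Four of the six safety-review triggers depend on grades that the plan does not define and that its only defined causality code cannot supply. This makes a stated safety rule unworkable as written; it is more than a missing detail.

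The exposure is limited to which events formally call a review. It is greatest for severe non-serious AEs. These feed the similar-severe-AE trigger, which starts at *possible*, but they receive only the investigator's two-way code. They are not generally referred to the DMC, and the safety and hospitalization section only compiles them for trends.

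The conclusion rests on the ordinary meaning of possibly and on no other document supplying the grades. The documents give no rate of events with competing causes, so the number affected cannot be estimated. Confidence is high for the textual mismatch and lower for its practical effect.

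**What to change.** Reconcile Safety and hospitalization analysis, Overall Study Halting Rules and Assessment of Causality, so that the categories recorded by the investigator and the DMC are the same ones that the triggers read. Specifically:

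1. Define each category, and say where an event with equally likely causes falls.
2. State which categories count as *related* for the DMC vote that invokes the stopping rules.
3. State which categories count as *related* for the primary endpoint.

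Either direction could be made consistent: record grades, or reword the triggers to the two-way code. The causality level that should call a review is for the sponsor to set.

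The cost is wording in these sections and in the endpoint definition, and possibly one field on the AE and DMC forms if they do not already carry it. The number of formal safety reviews may change as a result.
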